## 2.4. Study Design

Overview of Study Design and Key Features	
 
The diagram illustrates the study design timeline from Week 0 to Week 28. It is divided into a Treatment Phase (Weeks 0-12) and a Follow Up Phase (Weeks 16-28). In the Treatment Phase, participants receive a double-blind study treatment every 4 weeks, either GSK3772847 or Placebo, at Weeks 0, 4, 8, and 12. Simultaneously, background therapy is reduced from LABA, Sal, and ICS at Week 0 to FP 500 BID at Week 2, and then further reduced to FP 250 BID, FP 100 BID, and FP 50 BID by Week 10. In the Follow Up Phase, participants receive LABA and ICS from Week 16 to Week 28. Visits are labeled V0 through V14, with an ETP Visit at Week 11.
	
Design Features	
 
The study is a Phase IIa, multicenter, randomised, placebo-controlled, double-blind, stratified, parallel group study.
 

Dosing	
 
Participants will have a two-week Run-in period in which they take a background therapy of fluticasone propionate (FP)/salmeterol 500/50 mcg BID.
 
Following run-in they will be randomised to receive four doses of either GSK3772847 or Placebo intravenously (Week 0, 4, 8 and 12) whilst initially still receiving background FP/Salmeterol 500/50 mcg BID.
 
At Week 2 background therapy will be changed to FP 500 mcg BID only. This will then be reduced by approximately 50 % every two weeks until complete FP discontinuation at Week 10.
 

Treatment Assignment	
 
Participants will be randomised in a 1:1 ratio to receive four doses of either GSK3772847 or Placebo administered intravenously every 4 weeks.
 
Randomisation will be stratified based on participants' baseline peripheral blood eosinophil count which is measured at screening (<150 cells/<math>\mu</math>L, <math>\geq</math>150 cells/<math>\mu</math>L), Randomisation will also be stratified according to whether participants consent to the sputum sub study.
 

Overview of Study Design and Key Features	
Interim Analysis	
 
The End of Treatment Phase Analysis will take place after all subjects have completed the week 16 visit, and will be considered an interim analysis for both efficacy and safety. There will be no modifications to dosing regimens, sample size or any other aspects of the trial based on this data, as all study assessments, apart from follow-up, will have already been completed.
 

## 2.5. Statistical Hypotheses

The primary null hypothesis ( $H_0$ ) for this study is that the ratio of the proportions of subjects with loss of asthma control from randomisation to Week 16 between GSK3772847 and placebo is unity.

$$H_0: \frac{\text{Proportion with loss of asthma control at Week 16 on GSK3772847}}{\text{Proportion with loss of asthma control at Week 16 on Placebo}} = 1$$

The alternative hypothesis ( $H_1$ ) for this study is that the ratio of the proportions of subjects with loss of asthma control from randomisation to Week 16 between GSK3772847 and placebo is not unity.

$$H_1: \frac{\text{Proportion with loss of asthma control at Week 16 on GSK3772847}}{\text{Proportion with loss of asthma control at Week 16 on Placebo}} \neq 1$$

## 2.6. Sample Size Calculations

With 70 evaluable participants per arm and assuming the true proportion with loss of control on placebo is 44%, the smallest observed difference that would lead to rejection of the null hypothesis (minimum detectable effect) is 36% corresponding to a proportion with loss of control on GSK3772847 of 28%.

As detailed in Section 2.1, there was a typographical error in the protocol which meant that minimum detectable effect was incorrectly reported as 31%, this has been corrected above.

### **3. PLANNED ANALYSES**

#### **3.1. End of Treatment Phase Analyses**

The End of Treatment Phase Analysis will be performed after the completion of the following sequential steps:

1. All subjects have completed the Week 16 visit or the Early Withdrawal visit
2. All required database cleaning activities have been completed and database release has been declared by Data Management.
3. All criteria for unblinding the randomisation codes have been met.
4. Randomisation codes have been distributed according to RandAll NG procedures.

Due to an inability to lock log forms used for collection of exacerbation data, the end of treatment phase analysis will be considered an interim analysis for both efficacy and safety. Any safety data collected for participants who have completed clinic visits after Week 16 will also be cleaned and included in the analysis.

All participants will have completed the active treatment phase of the study by the time of the interim, so no modifications will be made to the study as a result of the End of Treatment Phase Analysis. The Final Analysis is intended to be an analysis of safety data collected in the Post-treatment Follow-Up phase.

The sponsor will be unblinded to the results of the analysis.

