#### **3.2. Final Analyses**

The final planned primary analyses will be performed after the completion of the following sequential steps:

- All subjects have completed the study.
- All required database cleaning activities for data after Week 16/ Early Withdrawal as well as data collected on log pages have been completed.
- Final database release and database freeze has been declared by Data Management.

No unblinding will take place as part of the final analysis as all participants will have already been unblinded during the End of Treatment Phase Analysis.

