**12.6.3. Efficacy**

Loss of Asthma Control
Multiple Loss of Asthma Control

 
If a participant reaches loss of control for multiple reasons then all reasons will be reported. For any time to loss of asthma control analysis, the time of the earliest component of loss of control will be used.
 

Date of Loss of Asthma Control
Date of loss of control will be taken from the loss of control log page.

Diary Data

The vendor data captures the date on which the subject completes the diary (actual date of collection) rather than the date to which the questions relate. For example, in the morning diary subjects are asked ‘Did you wake up due to asthma symptoms’ and ‘when you woke up due to your asthma symptoms did you use any rescue bronchodilator?’ In the evening diaries subjects answer a question on daytime asthma symptoms and record the number of puffs of rescue medication used during the day. This means that the morning diary date in the raw data refers to the events during the previous night and that the evening diary relates to the events during the day time.
 
In order to ensure that correct observations are assigned to each four-week time period, measurements recorded in the morning diary will have 1 day removed in the analysis dataset to ensure that the date reflects the time period that the information related to. This adjustment is not required for evening diary as these are collected in the evening of the day to which they relate. Questions which this affects are those where the timepoint reference is MORNING:
 
 
Was evening dose taken?
 
Did you wake up due to asthma symptoms?
 
When you woke up due to your asthma symptoms did you use any rescue bronchodilator?
 
Number of puffs – night time
 
 
PEF assessments will not have the adjustment made as these reflect the PEF as assessed (so the PEF recorded in the morning diary is the PEF at that time).

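### Exacerbation log forms that feed the primary endpoint stay unlocked when the sponsor is unblinded, and Sections 3.1 and 3.2 disagree on whether the later run is the primary analysis

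*SAP*

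**What the plan says.** Section 3.1 sets four sequential steps for the end-of-treatment analysis. All required cleaning and database release (step 2) come before the unblinding criteria are met and the randomisation codes are distributed (steps 3 and 4). The section then gives its reason for treating this analysis as interim for both efficacy and safety: "Due to an inability to lock log forms used for collection of exacerbation data". It states that the sponsor will be unblinded to the results. Of the later analysis it says: "The Final Analysis is intended to be an analysis of safety data collected in the Post-treatment Follow-Up phase".

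Section 3.2 opens differently: "The final planned primary analyses will be performed after the completion of the following sequential steps". One of those steps is that cleaning of data after Week 16 or early withdrawal, "as well as data collected on log pages have been completed". It adds that no further unblinding is needed, because that happened at the end-of-treatment analysis.

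Three other places matter:

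- Section 2.3 makes a clinically significant exacerbation one of the four components of loss of asthma control.
- Section 12.6.3 fixes the source of the event date: "Date of loss of control will be taken from the loss of control log page".
- Section 12.10.5 marks the loss-of-control Tables 2.4 to 2.13 for both ETP and SAC. Section 12.10.3 defines SAC as the final analysis.

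**The concern.** The SAP concedes that a form feeding the primary endpoint cannot be locked when the codes are released, and then schedules completion of log-page cleaning after that release. The wording limits one category to data after Week 16 or early withdrawal but puts no date limit on log pages. Week 0-16 endpoint records are therefore left open to change once the first result is known.

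The SAP also does not settle what the final analysis is. If it is a follow-up safety analysis, there is one primary result. If it is the primary analysis, the primary result comes from a database completed after unblinding. Because the tables are scheduled at both points, both results can exist, and no sentence says which one counts.

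Two things are at stake: protection of endpoint status from changes made with the first result known, and a single result of record that cannot be chosen afterwards.

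**Working it through.** **The text side by side**

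| Question | Section 3.1 | Section 3.2 |
|---|---|---|
| What is the final analysis? | Follow-up safety | Primary analyses |
| When is cleaning complete? | All required cleaning before code release | Log-page cleaning complete before the final run, after unblinding |
| Are endpoint forms locked? | Not the exacerbation log forms | Freeze declared only at the final release |

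The label given to the Week 16 run does not resolve this. An interim for both efficacy and safety implies a later efficacy analysis, which does not fit a final analysis of safety only. The December 2018 RAP bound after the amendment has the same two sentences, so the amendment did not address it.

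Edits could reach the results by two routes. An exacerbation record changes endpoint status only for a participant who met no other component. A changed date on the loss-of-control page could alter the Weeks 0-6 results (Tables 2.8 to 2.11) and time to loss of control (Tables 2.12 and 2.13) without changing Week 0-16 status.

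**The plan's own threshold**

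Section 2.6 supplies the inputs: "With 70 evaluable participants per arm and assuming the true proportion with loss of control on placebo is 44" per cent. It states a minimum detectable effect of 36%, that is 28% on GSK3772847. Alpha is not given as a number. Two-sided 5% is assumed from the not-equal alternative and the 95% intervals.

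Pooled test: z = (p1 − p2) / √[p̄(1 − p̄)·2/n]. With p1 = 0.44 and n = 70, z reaches 1.96 at p2 = 0.281, a relative reduction of 36.2%. The log-odds version gives 0.280 (36.4%). Directly, (0.44 − 0.28)/0.44 = 36.4%. The stated figure reproduces.

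**One event near that threshold (assumed counts)**

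44% of 70 is about 31 placebo events.

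- 31 v 19: difference 12/70 = 0.1714; p̄ = 50/140 = 0.3571; SE = 0.0810; z = 2.12; p = 0.034 (log-odds Wald 0.036).
- 31 v 20: difference 11/70 = 0.1571; p̄ = 51/140 = 0.3643; SE = 0.0813; z = 1.93; p = 0.053 (log-odds Wald 0.055).

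The primary analysis is Bayesian. Its posterior was approximated by independent Beta(x, n − x) draws, without the eosinophil covariate. The same one-event change moves P(ratio<1) from 0.984 to 0.975 and P(ratio<0.7) from 0.72 to 0.65. Section 2.1 says the 0.7 cut-off was added to help internal decisions, but the SAP sets no posterior threshold for success.

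**The case against.** The strongest reply is step 2 of Section 3.1, which requires all required cleaning before the codes are released. A log form that runs across visits naturally stays open while follow-up continues to Week 28, and Section 3.2 may mean only finishing such forms. This stands in part. A reader might infer that Week 0-16 log data are first cleaned after unblinding, but the text does not say so. It supports *not locked*, and later cleaning *not limited by date*. If the Week 0-16 log data were fixed by then, however, unlockable forms would be no reason to call the efficacy analysis interim. Section 4.1 shows that the SAP can require review before unblinding: it does so for protocol deviations.

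Other objections also narrow the point:

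- Only the exacerbation forms are named as unlockable. The loss-of-control page is reached only through the general reference to log pages in Section 3.2 together with Section 12.6.3.
- A reader might infer that people who know the allocation will edit endpoint data. The SAP says the sponsor is unblinded to the results. It does not say who can change log entries or whether sites receive allocations, and those controls may sit in documents not at hand.
- The ETP/SAC flags are imperfect evidence of a deliberate second primary analysis. PK Figures 6.1 to 6.4 carry both, although Section 9 excludes PK outputs from the end-of-treatment analysis. Yet the column can restrict a delivery, as the SAC-only PK tables show, and Section 3.2 itself uses the word *primary*.
- Some traceability exists: separate reporting areas for the two runs (Section 12.5.1), and Listing 34 at both deliveries. Comparing them would show that status or timing had changed, but not when or why, and would not say which result governs.
- Naming the final, frozen run as definitive would also end the ambiguity. It would not protect Week 0-16 records from change after unblinding.

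That no design change follows from the interim answers a worry about adaptation. It does not bear on data integrity or on the result of record.

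**Conclusion.** The point holds in limited form and should be corrected. The conflict between Sections 3.1 and 3.2 is plain on the page, no governing run is named, and Week 0-16 exacerbation records are left open to change after unblinding.

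The size of any effect cannot be estimated. The SAP does not say how many records might change or how many participants would have exacerbation as their only component. A reader might take the one-event example to mean that the trial's conclusion would be reversed. It shows only that a borderline supportive test is sensitive to a single record, under assumed counts, two-sided 5% and no covariate. Nor is this a group-sequential alpha problem: the treatment phase is complete at the first analysis and nothing in the design depends on it.

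**What to change.** Amend Sections 3.1 and 3.2 as follows.

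1. Between database release and distribution of the randomisation codes, take a dated, archived snapshot of the cleaned Week 0-16 exacerbation and loss-of-control log records. The cleaning is already required by step 2; the snapshot is new and does not need the forms to be locked.
2. Name the end-of-treatment analysis on that snapshot as the result of record for Tables 2.4 to 2.13.
3. Label any SAC re-run of those tables as a sensitivity analysis. Accompany it with a listing of every post-unblinding change to a Week 0-16 log record, giving the date, the reason and the effect on endpoint status.
4. Delete *primary* from the opening sentence of Section 3.2 so that it agrees with Section 3.1.

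The cost is SAP wording, one data snapshot and one listing, with no new data. The small downside is that a genuine late correction would appear only in the sensitivity run, where the listing would make it visible.

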#### **3.2. Final Analyses**

The final planned primary analyses will be performed after the completion of the following sequential steps:

- All subjects have completed the study.
- All required database cleaning activities for data after Week 16/ Early Withdrawal as well as data collected on log pages have been completed.
- Final database release and database freeze has been declared by Data Management.

No unblinding will take place as part of the final analysis as all participants will have already been unblinded during the End of Treatment Phase Analysis.

#### 4. ANALYSIS POPULATIONS

Some participants are being excluded from the efficacy analyses due to a failure at their site to follow GCP. As these participants received GSK3772847 or placebo during their period of participation, all safety data will be reported.

Population	Definition / Criteria	Analyses Evaluated
Enrolled	
 
The All Subjects Enrolled (ASE) population will consist of all participants who sign the ICF.
 
	
 
Study population
 
Reason for withdrawal prior to randomisation
 

Randomised	
 
The randomised population will consist of all participants who were randomised. A participant who is recorded as a screen or run-in failure and also randomised will be considered to be randomised in error provided they have not performed any study assessments.
 
	
 
No formal analysis will be performed on this population
 

Modified Intent-to-Treat excluding GCP non-compliant subjects (Loss of Control)	
 
The Modified Intent-to-Treat excluding GCP non-compliant subjects (Loss of Control) (mITT_LoC) will consist of all randomised participants who take at least 1 dose of study treatment, excluding participants where an investigation by GSK has shown that good clinical practice has not been followed. Any participants excluded from this population will be identified as protocol deviations and listed in a separate output. Participants will be analysed according to the treatment they receive <math>\geq 50\%</math> of the time. If the participant receives 50% of each treatment they will be analysed according to the randomised treatment. For loss of asthma control, participants will be analysed according to the treatment they were receiving at the time of loss of control.
 
	
 
Efficacy (loss of control)
 

Modified Intent-to-Treat excluding GCP non-compliant subjects	
 
The Modified Intent-to-Treat excluding GCP non-compliant subjects (mITT) population will consist of all randomised participants who take at least 1 dose of study treatment, excluding participants where an investigation by GSK has shown that good clinical practice has not been followed. Any participants excluded from this population will be identified as protocol deviations and listed in a separate output. Participants will be analysed according to the treatment they receive
 
	
 
Efficacy (all except loss of control)
 

Population	Definition / Criteria	Analyses Evaluated
	>=50% of the time. If the participant receives 50% of each treatment they will be analysed according to the randomised treatment.	
Safety including GCP non-compliant subjects	
 
The Safety (SAFF_ALL) population will consist of all randomised participants who take at least 1 dose of study treatment. Participant will be analysed according to the treatment they receive >=50% of the time. If the participant receives 50% of each treatment they will be analysed according to the randomised treatment.
 
	
 
Study population
 
Inclusion, exclusion and randomisation criteria deviations
 
Participant disposition
 
Safety
 

Pharmacokinetic	
 
The PK population will consist of all randomised participants who received at least one dose of study medication, and for whom at least one pharmacokinetic sample was obtained, analysed and was measurable.
 
	
 
PK
 

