**Table 1 Changes to Protocol Defined Analysis Plan**

Protocol	Reporting & Analysis Plan	
Statistical Analysis Plan	Statistical Analysis Plan	Rationale for Changes
Modified Intent to Treat population.	Modified Intent to Treat (Loss of Control), Modified Intent to Treat and Safety excluding GCP non-compliant subjects populations.	The Modified Intent to Treat (Loss of Control) was added to account for the intercurrent event when participants receive the wrong study treatment. Whilst the data from GCP non-compliant participants should not be used in the efficacy analysis, the participants were dosed with GSK3772847 or Placebo so all safety data (AEs, SAEs, ECGs etc.) should be reported.
Section 10.4.1 of the protocol describes a sensitivity analysis where data is analysed as missing and worst case (loss of control) for participants who withdraw from the study for reasons other than loss of asthma control.	A primary and secondary estimand have been defined to capture where data is analysed as missing and worst case (loss of control) for various intercurrent events where participants withdraw from the study for reasons other than loss of asthma control.	The protocol was approved before the ICH E9 addendum on estimands. The RAP is performing the same planned analysis as detailed in the Protocol however the terminology has been updated in accordance with ICH E9.
Statistical analysis would be performed for each screening eosinophil strata separately.	Bayesian analysis will include screening eosinophil strata as a covariate instead of performing split analysis models.  In addition, an exploratory analysis using fractional polynomials was added to examine the relationship between loss of control and screening eosinophils (continuous), IgE and FeNO.	Bayesian analysis will now include the same covariates as the frequentist analysis.  By modelling eosinophils as a continuous endpoint, it will provide more information on the impact of varying screening eosinophil levels on the treatment effect. It will also provide additional information on the role of IgE and FeNO on loss of asthma control.

Protocol	Reporting & Analysis Plan	
Statistical Analysis Plan	Statistical Analysis Plan	Rationale for Changes

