**NOTES :**

- Please refer to [Appendix 10](#): List of Data Displays which details the population to be used for each display being generated.
- If a participant is inadvertently given both study treatments they will be analysed according to the treatment that they received the more frequently.

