#### 7.1.3. Population of Interest

The primary efficacy analyses will be based on the modified Intent to Treat (Loss of Control) population, unless otherwise specified.

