### 12.6.2. Study Population

Age
Date of birth will be set as PPD YYYYY where YYYYY is the year of birth taken from the CRF. For participants who attended a screening visit, age will be calculated at the screening visit date. For pre-screen failures, age will be calculated at the pre-screening visit date.
Body Mass Index (BMI)
BMI = Weight (kg) / Height(m) 
Treatment Misallocations
To allocate treatment, the number of doses of GSK3772847 and Placebo that were given will be calculated, and the subject will be assigned to whichever treatment has the higher number. The only exception will be when both treatments were given equally, in which case the subject will be assigned their randomised treatment.
Early Withdrawal from Study Treatment Date

The eCRF captures the study treatment start and end, however this is the physical time and date of the infusion. The date of early withdrawal from study treatment is not captured and should therefore be calculated as follows:
 
 
• If the participant withdrew from treatment due to loss of asthma control then the date of early withdrawal from study treatment is set to the date of loss of asthma control.
 
• If the participant withdrew due to an AE/SAE/Death then withdrawal date is set to the AE/SAE onset date (all deaths should be reported as serious adverse events)
 
• If the participant withdrew from study treatment (for a reason other than those above) during the first 10 weeks of the study i.e. during the down titration of the background medications, then the FP/SAL or FP discontinuation date should be used as the date of withdrawal from study treatment.
 
• For participants who withdraw from study treatment (for a reason other than those above) between Week 10 and Week 16, there is no information on when they withdrew as they are no longer taking background medications. The date of early withdrawal from study treatment should therefore be set to the maximum of date of last dose of FP and date of last dose +1. This is because no more information is available other than the fact that they had not lost control prior to completing the down titration or prior to receiving their final dose of IP.
 

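### In the primary loss-of-control population, the arm of a participant given both treatments depends on whether the event occurs, other sections give a different rule, and no planned analysis uses the randomised arm

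*SAP*

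**What the plan says.** Section 7.1.3 fixes the population: "The primary efficacy analyses will be based on the modified Intent to Treat (Loss of Control) population, unless otherwise specified". Section 7.2.4.1 uses the same population for time to loss of control.

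Section 4 builds mITT_LoC in two steps. Participants first go to the treatment they received at least half the time, with an even split going to the randomised arm. That is then overridden: "For loss of asthma control, participants will be analysed according to the treatment they were receiving at the time of loss of control".

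Two other places cover the same people without that override. The note under Section 4 says: "If a participant is inadvertently given both study treatments they will be analysed according to the treatment that they received the more frequently". Section 12.6.2, on treatment misallocations, counts doses and says "the subject will be assigned to whichever treatment has the higher number". It names an equal split as the sole exception.

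Section 2.1, Table 1, gives the reason for the population: "The Modified Intent to Treat (Loss of Control) was added to account for the intercurrent event when participants receive the wrong study treatment". Wrong treatment does not, however, appear in the intercurrent-event table of Section 7.1.4. For the Randomised population, Section 4 states: "No formal analysis will be performed on this population". Tables 2.4 to 2.7 (Bayesian and frequentist, primary and secondary estimand) all use mITT_LoC.

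**The concern.** The override can apply only to participants who have the event. Anyone who received both treatments and kept control falls back on the majority rule. Among mixed-dosing participants, arm membership is thus settled after the outcome and by it. If misdosing runs mostly one way, events leave that arm while comparable non-events stay, and the ratio of proportions shifts.

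There is also a programming problem. Someone deriving the arm from Section 12.6.2 and someone deriving it from the mITT_LoC definition would build different primary datasets from the same data. Because every loss-of-control table uses one assignment, no planned result would show how much the choice matters.

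**Working it through.** **1. The rules side by side.** Take a participant randomised to GSK3772847 (A), with some placebo (P) infusions.

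| Doses received | Outcome | mITT_LoC definition | Section 12.6.2 | Randomised |
|---|---|---|---|---|
| A A A P | control kept | A | A | A |
| A A A P | lost after dose 4 | P | A | A |
| A P | lost after dose 2 | P | A (tie) | A |
| P | lost after dose 1 | P | P | A |

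Rows 1 and 2 have the same dosing and differ only in outcome, yet mITT_LoC puts them in different arms. Rows 2 and 3 show the conflict with Section 12.6.2. In row 4 the override changes nothing. A participant dosed as randomised throughout is in the randomised arm under every rule.

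**2. The plan's own figure.** Section 2.6 gives "With 70 evaluable participants per arm" and "assuming the true proportion with loss of control on placebo is 44" per cent, with a minimum detectable effect of 36%, i.e. 28% on GSK3772847. Section 2.5 has a two-sided alternative. The significance level is not stated in the SAP, so two-sided 0.05 is my assumption. With pooled variance,

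z = (0.44 − 0.28) / √[0.36 × 0.64 × (2/70)] = 0.16 / 0.0811 = 1.972, p = 0.0486.

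Solving for z = 1.96 gives 28.1% on active, a 36.2% reduction. The stated figure is reproduced.

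**3. One relabelled event near that limit.** In whole participants, 44% and 28% of 70 are 30.8 and 19.6, rounded to 31 and 20. Relabelling moves one participant, event included, from active to placebo.

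| | Placebo | Active | Ratio | Pearson p |
|---|---|---|---|---|
| As randomised | 31/70 | 20/70 | 0.645 | 0.053 |
| One active event relabelled | 32/71 | 19/69 | 0.611 | 0.031 |
| One placebo event relabelled | 30/69 | 21/71 | 0.680 | 0.088 |

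With flat beta(1,1) priors on each proportion (400,000 draws, a stand-in for the planned Bayesian logistic model), the first relabelling moves P(ratio<1) from 0.973 to 0.984, P(ratio<0.7) from 0.62 to 0.70, and P(ratio>0.6) from 0.65 to 0.56.

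**4. Average bias with no true effect.** Assume 44% in both arms, m participants randomised to active who received a minority of placebo doses, and a fraction f of their events falling in the wrong-dose interval. Expected relabelled events are v = m × 0.44 × f. The ratio from expected counts is [(30.8 − v)/(70 − v)] / [(30.8 + v)/(70 + v)]. Error rates come from 400,000 simulated trials per setting.

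| m | f | v | Ratio | Error favouring active | Two-sided error |
|---|---|---|---|---|---|
| 0 | – | 0 | 1.000 | 0.025 | 0.050 |
| 1 | 0.25 | 0.11 | 0.996 | 0.026 | 0.050 |
| 2 | 0.50 | 0.44 | 0.984 | 0.031 | 0.051 |
| 5 | 0.25 | 0.55 | 0.980 | 0.031 | 0.051 |
| 5 | 0.50 | 1.10 | 0.961 | 0.038 | 0.054 |
| 7 | 0.50 | 1.54 | 0.9455 | 0.046 | 0.058 |

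Misdosing in the placebo arm reverses the direction.

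**The case against.** The strongest reply is that the clause is narrow and possibly idle. It changes an arm only for someone who received both treatments and lost control on a treatment other than the one the majority or tie rule assigns. A reader might infer that randomisation is broken across the primary analysis, but participants dosed as randomised are untouched. A reader might also infer from Table 1 that the clause is known to have operated. Table 1 says only why the population was created. It gives no number of wrong-treatment cases and does not say that any were mixed. Both limits stand.

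The worked example sits on the rejection boundary by construction, and the p-value of 0.053 partly reflects rounding 19.6 events up to 20. From that table only one direction of relabelling crosses 5%. The other gives 0.088, so it does not support a claim that one participant can tip the result either way. Nor is 5% the primary criterion: Sections 7.1.2 and 7.1.5.1 make the Bayesian posterior probabilities primary and the logistic test supportive. This too stands, though the posterior probabilities move as well.

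Listings 5, 35 and 37 would show planned and actual treatment, treatment at time of loss, and misallocations. Each reassignment would be visible, but a listing does not re-estimate the ratio.

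Finally, the note under Section 4 could be read as general text that yields to the specific clause. That is fair for the note. It is harder for Section 12.6.2, which allows one exception only, and that exception is not loss of control.

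**Conclusion.** The point holds for mixed-dosing participants: mITT_LoC assigns their arm according to the outcome, two other places give a conflicting rule, and nothing planned uses the randomised arm. Its realised size is unknown because the SAP states no count, and it may be nil. The average bias is small for one or two misdosed participants (null ratio 0.984 or closer to 1 in the settings examined). It is moderate only if several were misdosed in one direction. A single relabelled event near the detection limit still shifts the posterior probability of a reduction of more than 30% by about 0.08, and Section 2.1 says that threshold was added to assist internal decision making.

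These sizes rest on the Section 2.6 planning rates, an assumed two-sided 5% level, assumed values of m (0 to 7) and f (0.25 or 0.50), and beta priors in place of the planned model. The structural flaw and the conflict between sections rest on none of these. This should be fixed, but it is not grounds for rejecting the primary analysis.

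**What to change.** - **Section 4, mITT_LoC:** analyse by randomised arm. Replace the at-least-half rule and its tie rule as well as the time-of-loss sentence. Removing only the last would leave a rule that contradicts the randomised arm. A majority count is not a clean alternative: participants are withdrawn once control is lost (Section 2.1), so the event itself shortens the dose history being counted, as row 4 of the first table shows.
- **Note under Section 4, and Section 12.6.2:** state that these assignments do not apply to the loss-of-control analyses.
- **Section 7.1.4:** add receipt of the wrong study treatment to the intercurrent-event table, with data used as randomised.
- **Section 12.10.5:** keep treatment at time of loss as a sensitivity analysis, labelled as such.

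The other efficacy endpoints in mITT do not carry the time-of-loss clause and need no change on this ground.

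The cost is SAP wording, one derivation flag and one sensitivity table, with no new data. The downside is slight dilution of the estimated effect if some participants received the wrong infusion. The rule should be settled before the treatment codes are released.
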